4.3.7.3 Biomarker analysis

Blood sampling will consist of collecting an aliquot of approximately 2 x 5 ml blood serum at the visits as indicated above. The additional blood samples for the study will be taken, if possible, during daily routine while the patient will be in the hospital (V1 & 3). For the Follow-Up visit (V6), an additional puncture will be necessary to obtain the blood samples. The blood samples will be labelled with the patient study ID and sent to the laboratory for processing. Afterwards they will be sent to the laboratories of [name]. [name] and [name]. [name] at the Department of Biomedicine, University Hospital Basel for biomarker analysis. The biomarkers assessed in this study are mentioned in 3.1 “Hypothesis and primary objective”. The biomarkers analyzed are validated and can be used to monitor brain injury in SSICH[41-43]. NfL are highly specific structural proteins of neurons released by the disruption of axonal membranes and associated with the severity, activity, and treatment response in neuronal injury[44-46]. S100B is a non-specific marker for neuronal injury and the disruption of the blood-brain barrier which correlates with the infarction volume and clinical outcome in ischemic stroke and SSICH[47, 48]. GFAP is an intermediate filament protein expressed by astrocytes. GFAP levels are specifically higher among patients with SSICH than among patients with ischemic stroke when measured early after symptom onset[49].

We will use a novel assay to measure NfL which was developed in our Laboratory of Clinical

Neuroimmunology ([name]. med. [name]). The test is based on single-molecule array (SIMOA) technology for digital immunoassays, using the capture monoclonal antibody (mAB) 47:3, and the biotinylated detector mAB 2:1 from UmanDiagnostics (Umeå, Sweden), transferred onto the SIMOA platform. SIMOA has been shown to be more sensitive than conventional ELISA or ECL based assays to quantify NfL in serum[50].

S100B and GFAP will be measured in the laboratory of [name]. med. [name] (S100B) and [name]. med. [name] (GFAP) using a standardized immunoassay from frozen plasma samples via electrochemiluminescence (Roche Cobas Elecsys, Roche, Switzerland).

Interleukins (IL-1 α and β , IL-2, IL-4, IL-5, IL-6, IL-8, IL-10, IL-12p70, TNF-alpha) will be measured in the laboratory of [name]. med. [name] with electrochemiluminescent (ECL) immunosorbent assays (Meso Scale Discovery, Maryland 20877, U.S.A.). This platform allows for testing of multiple biomarkers in limited sample volumes.

The blood samples and aliquots are stored in an appropriate cooling system in a restricted area only accessible to the authorised personnel and handled under appropriate conditions.

4.3.7.4 Concomitant care

All additional treatment deemed necessary by the treating physician to address potential complications of SSICH are allowed. This includes antibiotics for any kind of infection (pulmonary, wound infection), antipsychotics in case of delirium, pain medication when needed, gastric acid inhibitors as addendum to pain medication, reversal of anticoagulation according to the guidelines but also re-surgery or secondary surgery if deemed necessary. All occurrences of such treatment will be documented within the clinical research file (CRF)/electronic CRF (eCRF).

4.3.7.5 Medical reversal of oral anticoagulation

Oral anticoagulation will be pharmacologically reverted according to the guidelines at the University Hospital Basel and the current guidelines for ICH treatment.

- Heparin and low molecular weight heparin will be reverted with protamin.
- Vitamin K antagonists will be reverted with 4-factor prothrombin complex concentrate and/or vitamin K.
- Rivaroxaban, Apixaban, Edoxaban and Fondoparinoux (DOACS) will be reverted with 4-factor prothrombin complex concentrate.
- Dabigatran (DOAC) will be reverted with Idarucizumab.

Based on our clinics standard operation procedures, after surgery anticoagulation is restarted if no new bleeding is demonstrated in the postoperative CT scan at the 3rd postoperative day. DOACS and VKA will be resumed on the 3rd or 4th postoperative day (depending on the patients GFR, if the GFR is >30 we restart on the 2nd day after surgery or if the GFR is <30 we restart on the 3rd day after surgery) if the patient is clinically stable and no new bleeding is seen on the postoperative CT scan.

Antiplatelet drugs (Aspirin/Clopidogrel/Prasugrel or Ticagrelor) will be handled as follows:

- Aspirin will be discontinued if used as primary prophylaxis and reinstated at the 3rd postoperative day. If Aspirin is used as secondary prophylaxis, no discontinuation is required.
- Clopidogrel will be discontinued before surgery and pharmacologically reverted if necessary with platelet concentrate or Desmopressin and then reinstated at the 3rd postoperative day.
- Prasugrel will be discontinued before surgery and pharmacologically reverted if necessary with platelet concentrate and then reinstated at the 3rd postoperative day.
- Ticagrelor will be discontinued before surgery and then reinstated at the 3rd postoperative day.

4.3.8 Expected biases to the study and measures taken to reduce them

Expected biases are mentioned under 3.3.2 “Methods of minimising bias”. All involved personnel will be trained for the procedures and conduct of the protocol, its interventions and visits.

4.4 Withdrawal and discontinuation

Participants, their respective legal guardian or next of kin in case the patient remains unable to consent, can withdraw informed consent for this study whenever they want. They are withdrawn from this study if they do not meet the inclusion criteria mentioned under 4.1 “Inclusion criteria”. If patients of childbearing age get pregnant during the course of this study, they will be converted to MRI imaging instead of CT imaging but will not be ruled out.

The data of participants withdrawing prematurely (e.g. withdrawal of informed consent) is vital for the validity of the results of this trial. Currently, no sufficiently powered studies have been published on the potential benefits of ES in SSICH and it will be crucial to analyse every last patient so that the conclusion drawn from this trial is based on best possible evidence from our sample. With that, we can guarantee that future patients receive treatment based on the best possible data. The data and biological material of patients withdrawing prematurely will remain coded and used for the final outcome analysis according to the intention-to-treat principle. Participants lost that way will be marked as lost to follow-up.

5.1.1 Hypothesis

The **Null hypothesis (H₀)** describes no difference in functional outcome rates of early minimally invasive image-guided endoscopic evacuation additionally to BMT for SSICH compared to BMT alone.

The **Alternative Hypothesis (H₁)** describes a difference (either improved or worsened [two-sided testing]) functional outcome rates of early minimally invasive image guided endoscopic evacuation additionally to BMT for SSICH compared to BMT alone.

5.1.2 Sample size estimation

5.1.2.1 Derivation of assumptions for analysis of power

The power analysis is based upon the results from our own systematic review with meta-analysis, which assessed the effects of endoscopic surgery on functional outcome and mortality rates compared to BMT and CC in existing RCTs. A total of 591 patients with 312 in the control group (216 CC and 96 BMT) and 279 in the treatment group (ES) were analysed.

Favourable outcome, defined as mRS 0-3, Barthel Index ≥ 70 , Glasgow outcome scale 4-5 or an Activity of Daily Living score 1-3, 6 months after treatment was assessed as primary outcome. Favourable outcome of ES compared to BMT could be assessed in 2 studies yielding 23/64 for ES and 18/92 for BMT. This results in a cumulative Relative Risk (RR) of having a favourable outcome of 1.93 [1.12;3.33] ($p=0.02$) in favour for ES compared to BMT with insignificant heterogeneity (0%, $p=0.92$). However, we also looked at the sparse literature regarding ES in

SSICH treatment.

Yao et al. conducted the first review with meta-analysis on RCTs and cohort studies clarifying the therapeutic effects of ES in SSICH compared to a combined control of CC and BMT[24]. The primary outcome was all cause mortality while secondary outcomes were poor functional outcome (mRS 4-6, Glasgow Outcome Scale 1-3 or corresponding clinical presentation) among others.

Poor functional outcome was observed in 197/348 cases in ES and 271/373 in the control resulting in a RR of having poor outcome of 0.78 [0.70;0.87] ($p < 0.001$) with an insignificant heterogeneity (0%, $p = 0.60$) in favour of ES. The reciprocal value of this would correspond to a RR of having a favourable outcome of 1.28 in favour of ES.

We also included a work by Sondag et al., who compared all surgical treatment (craniotomy, craniopuncture, stereotactic aspiration, MISTIE and ES) to BMT in RCTs regarding favourable functional outcome and death[19]. Favourable functional outcome was defined as good outcome, described as mRS 0-3, Glasgow Outcome Scale 4 and 5, BI ≥ 60 and an extended Glasgow Outcome scale of 5-8 points or, if none of this scores was reported, according to the definition of favourable outcome defined by the authors of the included studies. If available, the outcome assessed at 6-month follow-up was assessed, if not available the 3- or 12-month follow-up was assessed together with the 6-month outcome for the meta-analysis. A subgroup analysis comparing MIS (stereotactic aspiration, MISTIE and ES) versus BMT alone showed an RR of 1.47 to achieve favourable outcome in favour of MIS (MIS events: 575/1056, BMT events: 378/989).

When combined, the RRs of our, Yao et al.'s and Sondag et al.'s work results in a RR of 1.56 or roughly **RR of 1.6**. Additionally, we analysed the favourable outcome rates (mRS 0-3 after 3 months) of BMT from 2020-2022 from the swiss stroke registry and found, that the rate of favourable outcome of the last two years was approximately 65%. However, all patients, even those with minimal bleeding and minimal impairment alongside patients with bleedings of >100 mL and very poor outcome, are included in the swiss stroke registry, potentially diluting the functional outcome in favour of good outcomes rather than worse outcomes. In consideration of that aspect, a plausible assumption for the proportion of positive outcomes in the control arm is 50% (0.5).

5.1.2.2 Bayesian Sequential analysis

Based on the to-date available literature[19, 23, 24], our own meta-analysis and the data of 2020-2022 derived from the Swiss stroke registry we assume a favorable outcome around 50% for patients treated with BMT, while we anticipate a positive risk ratio of 1.6 towards favorable outcome for ES compared to BMT. Based on these assumptions, we explored sample sizes needed for achieving “compelling evidence”, as described by Schönbrodt & Wagenmakers[51]. Compelling evidence is defined as finding a Bayes Factor (BF) that points with a certain strength at favoring the null hypothesis or the alternative hypothesis i.e. hypothetical experiments, expressing how much more likely the data were generated from a model where both study arms have the same probability of a positive outcome, compared to a model where there is a difference in the probability of a positive outcome. Simply put, it essentially measures the evidence between the two hypothesis. The BF expresses how likely the data originates from one hypothesis vs. the other (For an introduction into the interpretation of Bayes Factors as indices of evidence, please refer to Jarosz & Wiley[52]). Often used verbal interpretations are “substantial” or “positive” for BFs around 10, and “strong” to “very strong” for BFs over 100. Of all the strengths when using BF as opposed to p-values for inference, two stand out:

- A BF may quantify evidence against or in favor of the null-hypothesis.
- BFs may be monitored continuously as the data is generated and collected without the need of correction schemes as needed in a classical null-hypothesis significance testing procedures.

Both strengths described above are exploited in the sample size analysis performed here: we peak at the data at any moment to see whether we have enough evidence, to allow to decide in favor of either the alternative, or the null hypothesis. Note that it does not make sense to additionally calculate a p-value at the finally achieved n. Such a p-value will, by nature, be biased towards “significance”.

5.1.2.3 Bayesian A/B Test

We calculated the BF using the method presented by Gronau et al.[53] as implemented in the R package `ab_test`. For these first exploratory simulations, we used the default parameter priors supplied by the R package. The Bayes Factor calculated in this way, quantifies how much more likely the data originate from a “truth” where the probability in both arms is equal, vs a truth where both probabilities are different.

5.1.2.4 Stopping rule

The evidence is regularly calculated until either a pre-set level of evidence threshold, is achieved in favour of either of the hypotheses, or when the maximum sample size is reached. For the current study, we chose to set the maximum total sample size at 200, and the evidence threshold at a Bayes Factor of 10, which is generally considered as strong evidence. In the simulations below, however, we show the expected evidence up to 170 patients per arm.

5.1.2.5 Sample size analysis results

Figure 3 shows the results of a simulation, in which for various proportions of positive outcome for BMT (0.4, 0.5, 0.6, different panels) and various assumed positive risk ratios in favor of ES over BMT (1.2, 1.3, 1.4, 1.5, 1.6, differently colored lines), a large number of hypothetical trials were simulated, collecting up to 170 observations per study arm. The lines indicate the proportion of such simulated trials that reached the BF threshold of 10 in favor of either the null or the alternative hypothesis at each sample size.

Comparing the panels, one can see that, the higher the probability in the control arm, the quicker the percentage of trials that achieved the BF-threshold rises. In other words: the higher the baseline proportion of good outcome in the BMT arm, the lower the expected sample size. Comparing differently colored lines within panels, one can see that with higher risk ratios, the expected n decreases.

Systematic reviews as well as data analyzed from the Swiss Stroke Registry over the last 2 years suggests that a plausible assumption for the proportion of positive outcomes in the control arm is 50% (0.5) (Figure 2b). The pink line indicates the anticipated risk ratio of 1.6 in favor of ES. Based on our calculations after collecting data of 70 patients per study arm, about 90% of trials will have achieved a BF of 10, being the “Bayesian equivalent” to a power of 90%. In addition, 50% of the simulated trials already achieve this level of evidence after the 40th hypothetical patient (per arm). Further, based on these calculation, it is extremely unlikely that the trial would take more than 130 patients per arm. Based on these results we assume that we will likely be able to stop collecting data before reaching **75 patients per arm (total of 150 patients) to reach a BF of 10.**

[figure not shown]

Figure 3: Results of the simulation for SSE at different probabilities and Risk Ratios. A) For a probability of favorable outcome in BMT of 40%; B) for a probability of 50% and C) for a probability of 60%

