5.1.2.6 Conclusion of sample size estimation

Based on these results we assume that we will likely be able to stop collecting data before reaching **75 patients per arm (total of 150 patients) to reach a BF of 10**. We aim to collect a minimum of 40 patients per study arm. From that point on, we will perform the abovementioned BF test after every 40 new patients (about 20 per arm, exact number subject to randomization). The evidence is regularly calculated until either a pre-set level of evidence threshold is achieved in favor of either of the hypotheses (BF of 10 or 1/10 respectively, considered as strong evidence), or when the maximum sample size is reached. For the current study, we chose to set the maximum total sample size at 200 (as deemed sufficient based on a frequentist sample size estimation for the same assumptions). If this threshold is not reached, a new cost-benefit analysis of continuing to collect data will be performed. However, as described above, this is highly unlikely. After data collection is deemed completed and follow-ups at 6 months are complete, all secondary and sensitivity analyses will be performed. For the data collected up to 40 per arm, a p-value may be calculated (sensitivity analysis) and used for a classical hypothesis test.

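### The 90% by 70 per arm assumes that a risk ratio of 1.6 holds at a 50% control rate (80% in ES, odds ratio 4); the protocol's own counts point to 66–70% in ES

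*Protocol*

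**What the plan says.** Section 5.1.2.1 builds the effect from three sources.

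- The sponsor's own meta-analysis of ES against BMT, "yielding 23/64 for ES and 18/92 for BMT", has a stated RR of 1.93.
- A review of ES against craniotomy and BMT combined reports poor outcome in 197/348 against 271/373, an RR of 0.78. The protocol then says: "The reciprocal value of this would correspond to a RR of having a favourable outcome of 1.28 in favour of ES".
- A review of all minimally invasive surgery against BMT ("MIS events: 575/1056, BMT events: 378/989") has a stated RR of 1.47.

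Combining them "results in a RR of 1.56 or roughly RR of 1.6". The control rate of 50% is a judgement: a 3-month registry figure of about 65% is lowered because the registry takes all patients. Section 5.1.2.5 adds that systematic reviews also suggest 50%.

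Section 5.1.2.2 puts the two together: "we anticipate a positive risk ratio of 1.6 towards favorable outcome for ES compared to BMT". Section 5.1.2.5 then reports: "Based on our calculations after collecting data of 70 patients per study arm, about 90% of trials will have achieved a BF of 10". It expects to stop before 75 per arm, and the synopsis repeats this. On not reaching the threshold by the maximum of 200, section 5.1.2.6 says: "However, as described above, this is highly unlikely".

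**The concern.** A risk ratio does not carry freely between baselines. On a 20% control rate, 1.6 means 32%, a gain of 12 points. On a 50% control rate it means 80%, a gain of 30 points. All three sources have control rates well below 50%, and the protocol does not discuss whether the RR carries over.

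At stake is what the ethics committee, the funder and the monitoring board are told about the chance of a conclusive result. The 90%, the expected stop before 75 per arm and the confidence about 200 patients all rest on this one step. Section 5.1.2.6 also supports the 200 maximum by a frequentist calculation on the same assumptions.

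**Working it through.** **1. The plan's own figure.** Inputs: control 50%, ES 0.5 × 1.6 = 80%, threshold 10 or 1/10, 1:1 allocation. The protocol uses the package's default priors without giving their values. I assume N(0,1) on the mean logit and N(0,1) on the log OR, with log OR = 0 under the null. With a check after every pair of patients, 90.4% of simulated trials reach the threshold by 70 per arm. The stated 90% is reproduced, which also supports the assumed priors.

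**2. The sources, from the counts in section 5.1.2.1.** For the second source, favourable = total − poor: 348 − 197 = 151 and 373 − 271 = 102. OR = [p1/(1−p1)] / [p0/(1−p0)].

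| Source | Control | ES or MIS | Crude RR | Difference | OR |
|---|---|---|---|---|---|
| Own meta-analysis | 18/92 = 19.6% | 23/64 = 35.9% | 1.84 | 16.4 points | 2.31 |
| ES vs craniotomy + BMT | 102/373 = 27.3% | 151/348 = 43.4% | 1.59 | 16.0 points | 2.04 |
| All MIS vs BMT | 378/989 = 38.2% | 575/1056 = 54.5% | 1.42 | 16.2 points | 1.93 |
| **Plan** | 50% | 80% | 1.6 | 30 points | 4.0 |

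The RR falls steadily as the control rate rises. It does so too if the stated RRs of 1.93 and 1.47 replace the crude ones (1.93, 1.59, 1.47). The difference and the OR are nearly stable.

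**3. Carrying the sources to a 50% control rate.** By OR, p1 = OR/(1 + OR): 1.93/2.93 = 65.9%, 2.04/3.04 = 67.1%, 2.31/3.31 = 69.8%. By difference: 50 + 16 = 66%. So the ES rate is about 66–70%, an RR of 1.32 to 1.40.

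**4. Chance of a Bayes factor of at least 10**, cumulative at the planned looks, same priors:

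| Control vs ES | 40 per arm | 60 | 80 | 100 |
|---|---|---|---|---|
| 50% vs 80% | 55% | 80% | 92% | 97% |
| 50% vs 70% | 18% | 35% | 48% | 60% |
| 50% vs 66.7% (OR 2) | 11% | 22% | 32% | 41% |
| 50% vs 66% | 10% | 20% | 29% | 37% |
| 38.2% vs 54.5% (largest source) | 9% | 21% | 29% | 38% |

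With a prior SD of 0.5 or 2 on the log OR, the figures at 100 per arm are 35% or 32% for 66%, and 57% or 54% for 70%. Under the N(0,1) priors the smallest Bayes factor possible at 100 per arm is 0.27, so 1/10 cannot be reached. Every trial that misses 10 therefore ends at neither threshold.

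**5. Frequentist cross-check.** n per arm = [1.96√(2p̄q̄) + 1.2816√(p0q0 + p1q1)]² / (p1 − p0)², where p̄ is the mean of the two rates and q = 1 − p. This is 90% power at two-sided 5%. Against a 50% control rate it gives 52 per arm for 80%, 124 for 70%, 173 for 67.1% and 201 for 65.9%. The maximum is 100 per arm.

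**6. The reciprocal.** 1/0.78 = 1.28 is the ratio of poor outcomes turned round (control to ES), not the ratio of favourable ones. The counts give 43.4/27.3 = 1.59. The protocol's mean is (1.93 + 1.28 + 1.47)/3 = 1.56. Corrected, it is (1.93 + 1.59 + 1.47)/3 = 1.66.

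**The case against.** The strongest reply is that the 90% is correct and openly conditional on 50% and RR 1.6, that Figure 3 also simulates RRs of 1.2 to 1.5 at control rates of 40%, 50% and 60%, and that section 5.1.2.6 provides a cost-benefit review if 200 patients do not suffice. All of that stands: this is a criticism of a planning assumption. But the conclusions in section 5.1.2.5, section 5.1.2.6 and the synopsis are drawn only from RR 1.6 at 50%.

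The background section also cites a 2.8 times greater likelihood of functional independence with evacuation within 24 hours. Its scale is not given and section 5.1.2.1 does not use it, so it does not support the 80%.

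A reader might infer more than the documents support:

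- **That the wrong reciprocal inflates the plan.** It does the opposite; corrected, the mean RR rises from 1.56 to 1.66.
- **That 6 in 10 trials would fail.** That holds near OR 2. The only source that compares ES with BMT alone has OR 2.31, which gives about 4 in 10. The other two are less direct (a mixed control; mixed techniques). A range is needed.
- **That a trial reproducing 16 points must end inconclusive.** With 50/100 in controls, 66/100 in ES gives a Bayes factor of 3.2, and 70/100 is needed to pass 10. But the trial may already have stopped at 40, 60 or 80 per arm.
- **That no review supports a 50% control rate.** Section 5.1.2.2 cites a further review whose control rate is not shown. What can be said is that the counts shown give 20–38%.

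**Conclusion.** The point holds as a defect in the planning assumption. RR 1.6 at a 50% control rate requires 30 points and OR 4.0, where the protocol's own counts show about 16 points and OR 1.9 to 2.3 and speak against a constant RR. At the ES rate these counts imply (66–70%), the chance of a Bayes factor of 10 is about 20–35% by 60 per arm and 37–60% by 200 patients. Roughly 4 to 6 in 10 trials would not reach it, so calling that highly unlikely is not supported.

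This rests on three assumptions: the OR or the difference carries to 50% better than the RR does, the control rate really is 50%, and the default priors are N(0,1). Prior SDs of 0.5 and 2 lower the figures at 200 patients somewhat, to 32–57%.

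The reciprocal is a separate and minor error with no part in the shortfall.

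**What to change.** - In section 5.1.2.1, replace 1.28 by 1.59 and update the combined RR.
- Derive the ES rate on the OR or difference scale, or justify why the RR should stay at 1.6 on a 50% control rate.
- In sections 5.1.2.5 and 5.1.2.6 and the synopsis, report the chance of a Bayes factor of 10 at the planned looks and at 200 patients for ES rates of about 66–70%. Keep 80% as a scenario labelled optimistic, and state the prior values.
- Remove the statement that missing the threshold by 200 is highly unlikely, and qualify the expectation of stopping before 75 per arm.
- Reconcile the statement that systematic reviews suggest a 50% control rate with the 20–38% in the counts shown.

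The cost is a rerun of an existing simulation and some rewording; Figure 3 already covers RRs of 1.3 and 1.4 at 50%. Sample size, analysis and stopping rule need not change. The drawback is that the stated figures become less favourable.
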